All eligible women, in whom UFE is not inherently contraindicated, will be screened based on the following Inclusion/Exclusion criteria during their initial clinic appointment to discuss UFE. This will consist of a standardized questionnaire administered with participation from the primary physician and utilize standardized teach-back techniques to ensure patient understanding [24].

Inclusion: Women aged 20-50 years, undergoing UFE for symptomatic fibroids.

Exclusion: Women aged <20 or >50 years, those pregnant or actively attempting to conceive, those deemed mentally impaired to make their own medical decisions, previous documented allergy to dexamethasone, those currently taking daily steroids for any reason, those with diabetes or deemed to be pre-diabetic, those with contraindications for angiography, and prisoners.

9. Number of Subjects*

The power calculation is primarily based on the paper from Kim et al, which evaluated the effect of IV dexamethasone for treatment of post UFE pain and PES [3]. Based on this study, the mean Visual Analogue Scale for the Dexamethasone group was 2.89 (SD 1.09) compared to 3.91 (SD 2) for controls. However, in contrast to the reference study, the proposed study utilizes intraarterial drug delivery directly into uterus instead of IV route drug, which results in higher concentration in the uterus [25-27]. For a low flow organ such as uterus, intraarterial delivery of a low clearance drug such as dexamethasone will result in a regional advantage of 10-25 times compared to IV or oral delivery as shown by Daemen et al. [25]. Given the significantly enhanced organ drug concentration in the uterus, an increase in effect size of at least 50% is expected with intraarterial drug administration compared to IV route. To detect a difference 50% larger between control group and intervention group, using a two-sample t test with significance level of 0.05, sample size of 21 per group will provide us with 86% statistical power to detect such an effect size.

10. Study-Wide Recruitment Methods*

As with the discussion of Inclusion/Exclusion criteria, participants will be introduced to the study at the time of their initial clinical visit (referred for UFE through typical channels), and once they have already met criteria for undergoing a UFE for symptomatic fibroids. The patients will not be actively recruited for this study, per say, but will be offered admission to it providing they meet criteria.

11. Study Timelines*

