We intend to start the study by 10/2020 and to complete recruitment in 2 years, completing in 10/2022

Unless a patient chooses to opt-out of the study, a participant's duration will be limited to a total of 15 days beyond the procedural date. This will include periodic assessments of a subjective and objective measure, as outlined later in this proposal.

[figure not shown]
Enrollment and data analysis will be conducted on a rolling basis and deemed complete upon either meeting the primary endpoints (detailed below) or in the face of severe adverse events related to the procedural modification (detailed below).

12. Study Endpoints*

Primary end point of this study is post procedure pain. As such, pain is measured using a modified Visual Analogue Score (VAS), a numerical rating system that each patient assigns to their level of pain, at a particular time [28]. The study endpoints will include qualitative and quantitative collection of data. Pain following UFE is subjective and unique to each patient and can be based on the location, number of the fibroid(s) and the volume of fibroid(s). A modified VAS, termed *UFE Pain and PES Survey*, will be utilized to assess pain prior to and following the procedure (Pre, immediately after the procedure, and periodically for the next 13 days, as described below). Our primary endpoint will be a 3-point decrease in the UFE Pain & PES score between test and controls.

Secondary endpoints will include assessment of PES based on the measurement of nausea, vomiting, subjective fevers or chills, subjective data obtained from return to work times and readmission rates. This will be assessed in part using our *UFE Pain and PES Survey*, which includes a previously validated numerical scoring system

(0-3) to categorize nausea and vomiting, as well as a “Yes” or “No” scoring system to evaluate subjective fevers or chills.

13. Procedures Involved*

The Uterine Artery Embolization procedure with the proposed intervention is detailed below, italicized section denotes the interventions which are additions to the standard of care. The procedure is separated into Pre-Procedure Assessment and Imaging, Uterine Artery Embolization Procedure, and Post-Procedure Assessment and Imaging.

Pre-Procedure Assessment and Imaging:

- All accepted UFE study participants will be initially assessed using the attached UFE Pain & PES Survey to ascertain their current baseline pain.

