- *Pain, nausea, vomiting and fever will be documented using the visual analog score and nausea and vomiting score at:*
 - *Time 0 Immediately prior to the procedure*
 - *1 hour intervals for the first 3 hours*
 - *3 hour intervals for the next 9 hours*
 - *6 hour intervals for the next 12 hours*
 - *Daily, for the next 3 days*
 - *Once at day 7*
- *Each patient will complete uterine fibroid symptom & health-related quality of life questionnaire prior to the procedure and then 1 month and 3 month after.*
- Each patient will undergo post-procedural MRI imaging to determine residual fibroid burden and approximate volume at 3 months in order to gauge treatment response.
- PCA usage statistics.

Study Design:

This study is designed as a double blinded, placebo controlled randomized control trial. As previously mentioned, the study will divide the patients into two groups. The test group will receive intra-procedural intra-arterial dexamethasone and the control group, a saline placebo. Block randomization (Size: 8) will be done using a random number generator.

The drug or placebo will be prepared by research pharmacy and be delivered to the Interventional Radiology Department in identical containers with specific serial numbers. The physician performing the UFE, the patient and the research team will be unaware of the nature of the administered drug/placebo or the patient grouping. The drug preparation will be coordinated by the University of Miami Pharmacy Department's Research Coordinator, [name]. Once the uterine artery is catheterized, the drug or placebo will be injected intra-arterially. Embolization is then performed as usual.

Following UFE, all patients will be admitted to the general inpatient unit for observation, as is standard of care for all UFE patients. Following this observation period, patients will be discharged with appropriate instructions of when and how to follow-up with the treatment team. This will include explicit instructions to self-monitoring for unusual bleeding, swelling, bruising at the femoral artery access site, abnormal uterine bleeding, cramping, extended bouts of nausea, vomiting, fever, chills, and malaise. All patients will be given the number of an on-call physician for questions and concerns they may have. As mentioned above, all patients will be telephoned daily by a member of the research team on day 2, 3, 4, and 7 post-UFE.

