All patients will have a routine 2 week post-procedural phone call to review their symptoms, 1 month clinic visit and then 3 month clinic visit after MRI imaging.

All data collected from the Surveys will be stored and analyzed as described elsewhere in this proposal. Again, we expect that this study will reach its recruitment goal and Primary Endpoint in approximately 2 years.

To evaluate specific aim 1:

Pain will be assessed using 11 point visual analog scale as below:

The visual analog pain score will be documented as follows:

- Time 0 Immediately prior to the procedure
- 1 hour intervals for the first 3 hours
- 3 hour intervals for the next 9 hours
- 6 hour intervals for the next 12 hours
- Daily, for the next 3 days
- Once at day 7

First 3 of those surveys will be done in the recovery area. The amount of narcotic use from PCA pump will also be recorded.

To evaluate specific aim 2:

Post embolization syndrome will be assessed as reporting of nausea, vomiting and pain scores, that will be assessed at least twice during the day of the procedure and then daily for the next 3 days and then at 7 days. We will utilize our previously mentioned UFE Pain and PED Survey.

To evaluate specific aim 3:

Symptom relief, patient satisfaction and fibroid volume change will be measured through the completion of a UFE health-related quality of life (QOL) survey, UFE QOL Survey, prior to the procedure and then at 1 month and 3 month after procedure.

Uterine volume will be compared from the pre-procedure and 3 month post procedure MRI using volumetric software.

14. Data and Specimen Banking*

No specimen will be collected or stored. Data will be kept in password protected, HIPAA compliant University approved Box folder, accessible only to investigators.

15. Data Management*

All data will be stored, accessed, and analyzed utilizing server and computer workstations previously approved as HIPAA compliant. Data will be kept in password protected, HIPAA compliant University approved Box folder, accessible only to investigators. Anonymized data will include age, pre and post MRI imaging, UFE Pain & PES Survey, narcotic use, vital signs, subjective reports of nausea, vomiting, daily dietary intake, bowel movements, length of hospital stay, readmission rate, and days to return to baseline.

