A single computer system managed by the Pharmacology Research Coordinator, [name], will be maintained to ensure blinding of the cohorts. Collected data will be analyzed by [name], and done so prior to unblinding.

16. Provisions to Monitor the Data to Ensure the Safety of Subjects*

All data will be analyzed as it arrives and on a rolling basis by the primary physicians and researchers directly involved in this study, to ensure that the clinical findings and participant reported responses to the Pain & UFE Survey are not deviating in a way that could lead to undue harm.

As stated previously, all participants will be admitted to the hospital for observation for the first 24 hours and discharged with 2-week clinical follow-up in place and the contact information of a research team member. All participants will be contacted daily for the first 3 days, then at 7 and 14 days following the procedure. Any adverse effects of safety issues would be discovered in this follow up.

At 6 months we will analyze the interim data for any difference in the efficacy of treatment between the groups. All data will be analyzed using IBM SPSS software. We will use Student's T test for analysis of continuous variables, Chi square test for categorical variables with significance level set at two tailed p value of <0.05.

Although we expect that this trial exposes the participants to minimal risk, we consider the following statistically-significant differences between the two arms to be grounds for immediate trial termination: excessive abnormal uterine bleeding, infection, and sepsis.

17. Withdrawal of Subjects*

Subjects will be immediately withdrawn if it is deemed at any time prior to the procedure date that they fall into any of the previously outlined Exclusion criteria, suffer an intra-procedural adverse reaction to the use of dexamethasone, or willingly choose to leave the trial at any time.

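### The 3-point primary endpoint does not match the 1.53 points that the sample size rests on, and no time or summary is named for the pain comparison

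*Combined protocol and SAP*

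**What the plan says.** Section 12 names post-procedure pain as the primary endpoint and then gives it a threshold: "Our primary endpoint will be a 3-point decrease in the UFE Pain & PES score between test and controls". It describes the survey as a modified VAS, and adds that the survey also carries 0–3 items for nausea and vomiting. Section 13, under specific aim 1, says: "Pain will be assessed using 11 point visual analog scale as below". The list that follows has one score before the procedure and 12 after it.

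Section 9 takes its planning values from a randomised trial of intravenous dexamethasone: "the mean Visual Analogue Scale for the Dexamethasone group was 2.89 (SD 1.09) compared to 3.91 (SD 2) for controls". It expects the intra-arterial route to raise the effect by half or more, and sets the target: "To detect a difference 50% larger between control group and intervention group, using a two-sample t test with significance level of 0.05". With 21 per group it claims 86% power. The figure of 3 points does not appear there.

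The only analysis text is in section 16: Student's "T test for analysis of continuous variables, Chi square test for categorical variables with significance level set at two tailed p value of <0.05". It gives no time point, summary or repeated-measures model.

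Section 11 says that enrolment and analysis are complete once the primary endpoints are met, or if severe adverse events occur. Section 13 says: "we expect that this study will reach its recruitment goal and Primary Endpoint in approximately 2 years".

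On blinding, section 13 says that the operator, patient and research team "will be unaware of the nature of the administered drug/placebo or the patient grouping". Section 15 has the data analysed "and done so prior to unblinding".

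**The concern.** The sentence in section 12 leaves two things open.

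1. **The role of the 3 points.** They could be a threshold that the observed difference must reach, a true difference hoped for, or a mark of clinical importance. Section 12 calls them the primary endpoint, and section 11 ties completion of the study to meeting it, so a reader can fairly take them as a decision rule. If they are one, the stated 86% is not the chance of meeting it.
2. **What is compared.** Twelve post-procedure scores could give a difference at any one time, a mean, a peak, an area under the curve or a change from baseline. The plan describes one t test and does not say on which of these.

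The two gaps pull in opposite directions. A required observed 3 points makes a useful drug look like a failure. A p value below 0.05 at whichever time shows it makes an inactive drug look useful too often.

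**Working it through.** **Inputs.** Section 9: means 2.89 and 3.91, SDs 1.09 and 2, inflation of 50%, 21 per arm, t test at 0.05. Section 16: two-sided. Section 12: 3 points. Section 13: the score schedule.

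**Step 1: reproduce the 86%.**
- Difference = 1.5 × (3.91 − 2.89) = 1.5 × 1.02 = 1.53.
- Pooled SD = √((1.09² + 2²)/2) = 1.611.
- SE = 1.611 × √(2/21) = 0.497.
- Power at 1.53: 85.2% (noncentral t, 40 df), 84.6% (Welch), 86.8% (normal approximation). The plan says 86%, so it reproduces.
- Power at the uninflated 1.02 is 52%; at 3 it is above 99.9%. The sample size therefore rests on 1.53.

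**Step 2: compare with the endpoint (same scale assumed).**
- 3/1.53 = 1.96.
- From a control mean of 3.91, a fall of 3 is 3/3.91 = 77%, leaving 0.91.
- Smallest significant difference = 2.021 × 0.497 = 1.00 point.

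**Step 3: chance of observing at least 3 points**, 1 − Φ((3 − true difference)/SE):

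| True difference | SD | Chance |
|---|---|---|
| 1.53 | 1.61 | 0.16% |
| 2.04 (twice 1.02) | 1.61 | 2.7% |
| 2.5 | 1.61 | 16% |
| 3 | 1.61 | 50% |
| 1.53 | 2 (assumed) | 0.9% |
| 1.53 | 3 (assumed) | 5.6% |

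Even if any of the 12 times could count and 1.53 held at all of them, simulation gives 0.6% (correlation 0.9) to 1.8% (independent). With no true effect, 3 points is 3/0.497 = 6.0 SE, so false positives are not the problem under this rule.

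**Step 4: count the scores.** 3 hourly + 3 three-hourly + 2 six-hourly + 3 daily + 1 at day 7 = 12.

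**Step 5: if p<0.05 at any of the 12 were accepted.** Chance of a false claim for the drug, with equal correlation between times (assumed):

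| Correlation | False claim for the drug (planned 2.5%) |
|---|---|
| 0.9 | 6.7% |
| 0.7 | 11.6% |
| 0.5 | 16.0% |

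Independence gives 1 − 0.975¹² = 26%. This is a ceiling and not a realistic value for repeated scores from one patient.

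**Step 6: power of a single summary.** The trapezoid mean over 1–24 h uses the scores at 1, 2, 3, 6, 9, 12, 18 and 24 h, with weights 0.022, 0.043, 0.087, 0.130, 0.130, 0.196, 0.261 and 0.130. An effect lasting only 12 h contributes 14/23 = 0.609 of its size, so 1.53 × 0.609 = 0.93. The variance factor is ρ + (1 − ρ)Σw².

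| Measure and effect of 1.53 | ρ = 0.5 | ρ = 0.7 | ρ = 0.9 | SD 1.61 already that of a time average |
|---|---|---|---|---|
| 1–24 h mean, effect lasts 24 h | 98% | 93% | 88% | 85% |
| 1–24 h mean, effect lasts 12 h | 67% | 56% | 48% | 45% |
| 1–12 h mean, effect lasts at least 12 h | 97% | 93% | 88% | 85% |

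The first three columns assume that 1.61 is the SD of one score; section 9 does not say.

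**The case against.** Several points on the other side have force.

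- **Section 9 treats the 50% as a minimum.** Powering on a cautious difference while hoping for a larger one is not in itself a contradiction. This stands: a reader might infer that the trial is bound to miss its endpoint, and the documents do not support that. Step 3 shows how the chance rises with the true effect. What remains is that the role of the 3 points is unstated and that the 86% does not refer to them.
- **The scales may differ.** The 3 points apply to the survey score and the 1.53 to a VAS in another study. Section 12's description of the survey as a modified VAS supports one scale but does not prove it, since the form is not available. If the score is a composite with nausea and vomiting items, the ratio of 1.96 and the Step 3 figures do not apply. The endpoint and the power calculation would then be on different scales, which also needs correcting.
- **Nothing says that any time may count.** A reader might infer that the plan permits picking the best of 12 times. It does not say so; section 9 describes one t test. Step 5 measures a risk left open, not a stated rule. Blinding narrows that risk, but a between-group test needs at least coded groups, and these can be compared at every time.
- **The evidence for a success rule is limited.** Section 13's phrase about reaching the endpoint in two years could simply mean finishing data collection. Section 11 is the firmer support.
- **A time could be named elsewhere.** The general trial protocol appendix and the timeline figure are not available, so the gap is one in the visible text.

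**Conclusion.** The concern holds. If the primary score is the 0–10 pain scale, the endpoint threshold is 1.96 times the difference that gives the stated power. Read as an observed threshold, it would be met in about 0.2% of trials at a true 1.53 points, 2.7% at 2.04 and 16% at 2.5, although about 1.0 point is significant. These figures use section 9's SDs and 21 per arm. If the score is a composite, the mismatch is one of scale and cannot be sized from the documents.

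Separately, the visible text does not identify which of 12 scores, or which summary of them, carries the primary test. That gap does not depend on any assumption. Its possible cost, a false-claim chance of about 7–16% against 2.5%, rests on assumed correlations and on someone actually testing every time. The documents do not show that this was done or intended.

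**What to change.** In sections 12 and 16:

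1. State that the primary outcome is the 0–10 pain item, and name one summary of scores already scheduled. One example is the time-weighted mean over 1–24 h; another, if a shorter effect is expected, is the mean over 1–12 h. Section 7 describes pain as worst in the first 12 to 24 hours.
2. Define success as two-sided p<0.05 from the two-sample t test on that summary. Remove the 3-point criterion or reconcile it with the 1.53 points in section 9.
3. Make all other times secondary.
4. Fix and date this choice before anyone sees results by group, including coded groups and the 6-month efficacy look in section 16. Recruitment was due to end in 10/2022 and the latest revision is dated 09/12/2023, so such results may already exist; the documents do not say. If they have been seen, report the choice as post hoc.

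Minor: section 12 mentions a score straight after the procedure and follow-up over 13 days, whereas the score list in section 13 starts at 1 hour and ends at day 7. The two-week call may explain the longer period, but it is not in the score list. Reconcile them.

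**Cost.** No extra data are needed. The real trade-off is the window: a 1–24 h mean has only about 45–67% power if a 1.53-point effect lasts 12 h, while a 1–12 h mean keeps 85–97% but says nothing about later pain.

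### Return-to-work time is a time-to-event outcome, but the plan has no rule for women not back at last contact and gives inconsistent follow-up lengths

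*Combined protocol and SAP*

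**What the plan says.** - **Outcome.** Section 12 (Study Endpoints) includes "subjective data obtained from return to work times and readmission rates" among the secondary measures. Section 15 (Data Management) lists "length of hospital stay, readmission rate, and days to return to baseline" among the data held. Section 19 names faster return to work or baseline activity as a possible benefit.
- **Method.** Section 16, directly after the sentence on the 6-month interim look, gives Student's "T test for analysis of continuous variables, Chi square test for categorical variables", with "significance level set at two tailed p value of <0.05". No other analysis method appears in the document, and no test is assigned to return to work by name.
- **Follow-up.** Section 11 says a participant's "duration will be limited to a total of 15 days beyond the procedural date". Section 16 says participants will be "contacted daily for the first 3 days, then at 7 and 14 days following the procedure". Section 13 schedules a 2-week call and then a "1 month clinic visit and then 3 month clinic visit after MRI imaging", with quality-of-life questionnaires at 1 and 3 months.
- **Not stated.** There is no time origin for return to work, no contact at which it is asked, no censoring or missing-data rule, and no provision for women who were not working beforehand.

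**The concern.** A woman who has not gone back to work by her last contact has a censored time: it is known only to exceed that day. A t test needs a number for every woman it includes, and the plan does not say what number, if any, she receives.

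One natural default is to analyse only women with a recorded time. That selects on something that happens after randomisation. If dexamethasone speeds recovery, it also selects differently by arm, because more of the slow recoveries are removed from the control group. The estimated difference then shrinks towards zero.

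How much this matters depends on how many women are still off work at last contact, and so on which follow-up statement governs. What is at stake is a missed or understated benefit on a secondary measure that the protocol itself puts forward.

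**Working it through.** **1. The plan's own power figure.** It concerns pain only. Inputs from Section 9: means 2.89 (SD 1.09) and 3.91 (SD 2), difference enlarged by 50%, 21 per group, two-sided 0.05.
- Pooled SD = sqrt((1.09² + 2²)/2) = 1.611. Difference = 1.5 × 1.02 = 1.53. Standardised difference = 1.53/1.611 = 0.950.
- Noncentrality = 0.950 × sqrt(21/2) = 3.08. Power is 85.2% (t) or 86.8% (normal), against the stated 86%.

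The figure reproduces and nothing below changes it. No figure is stated for return to work.

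**2. Assumptions, none of them from the documents.** Return times are log-normal with SD of log s = 0.6 and median m. All 21 women per arm are eligible, and the last contact is at day h.

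**3. Formulas.** With a = ln(h/m)/s:
- true mean = m·exp(s²/2)
- share back by day h = Φ(a)
- mean among women back by day h = m·exp(s²/2)·Φ(a − s)/Φ(a)

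**4. Medians 14 (control) v 9 (dexamethasone), h = 14.**
- True means: 14 × 1.1972 = 16.76 and 9 × 1.1972 = 10.775, a difference of 5.99 days. Simulated values lie between 5.9 and 6.1.
- Control: a = 0, so 50% are back. Mean among them = 16.761 × 0.27425/0.5 = 9.19.
- Dexamethasone: a = ln(14/9)/0.6 = 0.736, so 77% are back. Mean among them = 10.775 × 0.5542/0.7693 = 7.76.
- Returners-only difference = 9.19 − 7.76 = 1.43 days, and 1.43/5.99 = 24% of the true difference.

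**5. Other cut-offs and medians.** Differences come from the same formulas. Power is simulated; a range shows the spread between repeat runs.

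| Medians | Last contact | Back by then | Returners-only / true difference (days) | Power, t test on returners | Power, log-rank |
|---|---|---|---|---|---|
| 14 v 9 | day 14 | 50% v 77% | 1.43 / 5.99 (24%) | 21% | 57% |
| 14 v 9 | day 30 | 90% v 98% | 3.83 / 5.99 (64%) | 48-49% | 58-59% |
| 14 v 9 | day 90 | over 99% in both | 5.90 / 5.99 (99%) | 58% | 58% |
| 10 v 7 | day 14 | 71% v 88% | 1.34 / 3.59 (37%) | 23-25% | 41-43% |

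**6. Sensitivity to the distribution.** Twelve scenarios were run: exponential, or log-normal with SD of log 0.5 or 0.8; control median 7, 10, 14 or 21 days; treated times 0.7 × control. Share of the true difference left among returners:
- day 14: 3% to 71%, below half in 11 of 12
- day 30: 11% to 98%, below half in 6 of 12
- day 90: 61% to 100%, below half in none

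With a control median of 10 days and a day-14 cut-off, power for the returners-only t test against log-rank is 6% v 16% (exponential), 36% v 55% (SD of log 0.5) and 13% v 26% (SD of log 0.8).

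**7. No treatment effect.** The returners-only t test rejects in 4.4% to 5.4% of trials, so false positives are not the problem. The large-sample log-rank test rejects in 5.1% to 6.1%, slightly above nominal at this sample size.

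**8. The other obvious handling.** Give each woman not yet back the last-contact day and keep her in the t test. The mean is then m·exp(s²/2)·Φ(a − s) + h·(1 − Φ(a)). For medians 14 v 9 and h = 14 this gives 11.60 − 9.20 = 2.4 days, with power 58-60%.

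**The case against.** A reader might infer that the planned test compares only returners and hides most of any benefit. The documents do not support either part as a statement of fact.

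- **Exclusion is not written.** No section says that women without a return date are dropped, and none assigns return to work to the t test. The Section 16 sentence is generic and also offers a chi-square test, which would suit back-at-work yes/no at a fixed contact.
- **The power loss comes from dropping women, not from the t test.** Step 8 shows that a t test keeping everyone, with the last-contact day filled in, has about the same power as log-rank (58% v 57%).
- **The day 14-15 cut-off is the harshest reading.** Section 13 has study questionnaires and clinic visits at 1 and 3 months, when a return date could be asked retrospectively. At 3 months the loss is negligible.
- **Some material cannot be seen.** The surveys are listed as appendices but their contents are not shown, and neither is the timeline figure. They may say when return to work is asked.

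All four points stand, and they make the harm conditional. They do not remove the gap. The text that can be read leaves the handling open, and that choice alone moves power between 21% and about 58% in the same data. Filling in the last-contact day still estimates only 2.4 of 6.0 days, because it measures a difference truncated at day 14. The later visits help only if the question is asked there, and Section 11 says participation has ended by then.

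**Conclusion.** The point holds as a gap in specification. Return to work and return to baseline are time-to-event outcomes; the plan offers only a t test for continuous variables, has no rule for women not back at last contact, and contradicts itself on how long women are followed.

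If follow-up for this item ends at day 14-15 and women without a date are left out, a real benefit could be understated by more than half. This occurs in 11 of 12 assumed scenarios; in the worked example 24% of the difference remains, with power 21% against 57%. At 1 month the loss is smaller and depends on the distribution. At 3 months it is negligible in the worked example and never exceeds half in the scenarios run.

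A claim that the plan will hide most of any benefit goes too far: it needs both the exclusion and the early cut-off, and the documents settle neither. All medians and spreads are assumptions. The error is understatement, not false positives; it concerns a secondary measure and leaves the primary pain endpoint and its 86% power untouched. It should be fixed before unblinding, but it is not critical to the trial.

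**What to change.** 1. Reconcile the follow-up statements in Sections 11, 13 and 16, and say which contact is the last for this item.
2. Define the outcome as days from the procedure to return to work among women working beforehand, or to usual activity for all women. The first choice lowers the number analysed, and with it the power of any method.
3. Ask for the calendar date of return at the already scheduled day 7, 2-week, 1-month and 3-month contacts.
4. Censor women not yet back at their last contact. Compare arms with a log-rank test, and report Kaplan-Meier medians and the proportion back by day 14. With about 42 women, a permutation p-value would deal with the slight excess over 5% seen in step 7. A rank test giving women not yet back the worst rank is an acceptable alternative.
5. State that all eligible randomised women stay in the comparison.

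The cost is a few sentences in the analysis section and one date question at contacts that already take place. No extra visits are needed.

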- Current medication requirements (e.g. OCPs, NSAIDs, narcotics, anti-emetics) will also be assessed at this time.
- Basic laboratory studies will be conducted at this time. This will include a Complete Metabolic Panel (CMP), Complete Blood Counts (CBC), Hemoglobin A1c, and qualitative urine pregnancy test (UPT).
- Each patient will further undergo (or have recent) pre-procedural imaging to determine fibroid burden, approximate volume, and arterial anatomy. This should be an MRI of the pelvis.

Uterine Embolization Procedure:

No changes are proposed to the standard UFE procedure except for the intraarterial delivery of dexamethasone.

Pre-UFE patients will receive the following medications for conscious sedation, pain control and nausea/vomiting during the procedure as per the standard departmental protocol, unless contraindicated:

- 50-300 mg IV Fentanyl
- 0.5- 3.0 mg IV Versed
- 30 mg IV Toradol
- 1 g IV acetaminophen

Procedure technique:

No changes are proposed to the standard UFE procedure except for the intraarterial delivery of dexamethasone.

Common femoral or radial artery access is used for the procedure. Using a combination of base catheters, microcatheters and different wires, each uterine artery is catheterized and angiograms are performed. *Following this, prior to embolization, 5 mg of IV dexamethasone or placebo are injected via the microcatheter placed in the uterine artery.* This is followed by particle embolization using particles of size ranging from 500-1000 μ M, until near stasis as per standard technique. The same procedure is then repeated on the contralateral uterine artery. Finally, catheters and sheaths will be removed and hemostasis achieved at the access sites using closure device or manual compression. Patients will be admitted to the general medicine ward for overnight observation.

Post-UFE patients will receive the following pain/anti-emetic regimen post procedure:

Inpatient Medications

- 30 mg IV Ketorolac q6h
- 650 mg PO Acetaminophen q6h (continued for 4 days post procedure)
- 0.2 mg demand dose, 10 minute lockout, 1.2 mg/hour, Hydromorphone PCA
- 4 mg IV Ondansetron q6h PRN

Discharge Medications

- 650 mg PO Acetaminophen q6h (4 days post procedure, then q12h)
- 800 mg PO Ibuprofen q6h (4 days post procedure, then q12h)
- 5/325 mg PO Percocet q6h PRN
- 100 mg PO Docusate Sodium (Colace) q12h (4 days post procedure, then PRN)
- 4 mg SL Ondansetron q6h PRN

Post-Procedure Assessment and Imaging:

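### Section 13 gives pre-procedure fentanyl in milligrams in the extracted text; the unit is very probably meant to be micrograms and should be checked and corrected

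*Combined protocol and SAP*

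**What the plan says.** Section 13 (Procedures Involved, under Uterine Embolization Procedure) introduces the sedation list as follows: "Pre-UFE patients will receive the following medications for conscious sedation, pain control and nausea/vomiting during the procedure as per the standard departmental protocol". The first item is "50-300 mg IV Fentanyl". No other section of the available text gives a fentanyl dose.

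The inpatient list in the same section gives the other intravenous opioid: "0.2 mg demand dose, 10 minute lockout, 1.2 mg/hour, Hydromorphone PCA".

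Three statements define the status of the fentanyl line:

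- The opening of section 13 explains its typography: "italicized section denotes the interventions which are additions to the standard of care". The fentanyl line is not italicised, so it is standard care and not a study addition.
- The sedation list applies "as per the standard departmental protocol, unless contraindicated". That departmental protocol is not among the documents.
- Section 13 also states: "No changes are proposed to the standard UFE procedure except for the intraarterial delivery of dexamethasone".

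The appendix list at the front names a General Trial Protocol, which is not reproduced in the available text.

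**The concern.** Two intravenous opioids appear in one section on very different scales. Hydromorphone is given in tenths of a milligram per demand, fentanyl in tens to hundreds of milligrams. A slip between milligrams and micrograms would explain this, and the factor would be 1000.

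What is at stake is patient safety. The line is an operative instruction about what enrolled patients will receive, and followed literally it would be dangerous. Nothing else in the available text would alert a reader to the correct unit.

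**Working it through.** **Inputs, all from section 13:** fentanyl 50-300 mg IV; hydromorphone PCA 0.2 mg per demand, 10-minute lockout, 1.2 mg/hour.

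**Step 1. Reproduce the plan's own figure.** Demands per hour = 60 / 10 = 6. Hourly amount = 6 x 0.2 = 1.2 mg. This equals the printed 1.2 mg/hour, so the PCA line is internally consistent and its milligram unit is coherent. The match also favours reading 1.2 mg/hour as the hourly limit.

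**Step 2. State the assumption.** Let r be the potency of fentanyl per mg relative to hydromorphone. The documents do not give r. The assumption is r of at least 1. The hydromorphone equivalent of a fentanyl dose is dose x r.

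**Step 3. Apply it to both readings, at the lowest allowed value, r = 1.**

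| Reading of the unit | Dose in mg | In PCA demands of 0.2 mg |
|---|---|---|
| Milligrams, as extracted | 50 to 300 | 50/0.2 = 250 to 300/0.2 = 1500 |
| Micrograms | 50/1000 = 0.05 to 300/1000 = 0.30 | 0.05/0.2 = 0.25 to 0.30/0.2 = 1.5 |

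Any r above 1 makes the milligram reading less plausible still. For the milligram range to match one PCA demand, fentanyl would have to be 250 to 1500 times weaker per mg than hydromorphone.

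**Step 4. Ask what the mass comparison shows without the assumption.** Over 24 hours the PCA limit is 24 x 1.2 = 28.8 mg. Other lines in the same sedation list also exceed that by mass: Toradol 30/28.8 = 1.04, and acetaminophen 1 g, 1000/28.8 = 34.7. Nothing suggests that those units are wrong. A mass ratio between different drugs therefore does not identify a unit error. The inference rests on the assumption in step 2.

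**Step 5. Consider a reading fault.** A micro sign does survive elsewhere in section 13, after the words "This is followed by particle embolization using particles of size ranging from 500-1000", though it prints irregularly, with a space and a capital M. Micro signs were therefore not lost throughout the section, which makes a misread of the fentanyl line somewhat less likely. It does not exclude one.

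**The case against.** The strongest objection is that the point turns on one character of text extracted from a PDF. If the PDF prints micrograms, the plan contains no error. This stands, and it is why the first action is to look at the original.

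A second objection is that the line is background to the trial. It is standard care, it defers to a departmental protocol, and that protocol lowers the practical risk. This also stands, and it limits the severity. It is not a reason to leave the line alone, because the sentence still says what enrolled patients will receive.

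A reader might infer that the arithmetic alone proves the error: set against a full day of PCA, 50/28.8 = 1.7 and 300/28.8 = 10.4. The documents do not support that.

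- Step 4 shows that the same test flags other lines in the list.
- The ratio depends on how the PCA line is read. If 1.2 mg/hour were a basal rate on top of the demands, the daily maximum would be 24 x 2.4 = 57.6 mg and the ratio 0.87 to 5.2, below 1 at the low end.
- The 24-hour window comes from section 16 ("all participants will be admitted to the hospital for observation for the first 24 hours"). Section 13 speaks only of an overnight stay, and neither section says how long the PCA runs.

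A reader might also infer that no correct dose exists anywhere in the trial's papers. The available text cannot show that, because the General Trial Protocol appendix and the departmental protocol are not in it.

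**Conclusion.** The concern holds as a minor patient-safety correction. In the extracted text, the only fentanyl dose in section 13 carries a unit that is very probably a thousand times too large: 50-300 mg where 50-300 micrograms (0.05 to 0.30 mg) is expected.

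This rests on two conditions. First, fentanyl is at least as potent per milligram as hydromorphone, which is general pharmacology and not stated in the documents. Second, the PDF itself prints mg.

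A reader might go further and infer that patients were or would be overdosed, or that the trial's results are affected. The documents support neither. Dosing defers to a departmental protocol, the comparison does not measure harm, and the line applies equally to both arms. It does not touch the endpoints, the sample size and power statement in section 9, or the analysis.

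**What to change.** Check the fentanyl line against the original PDF, the departmental sedation protocol that section 13 relies on, and the General Trial Protocol appendix. If the PDF prints mg and those sources confirm the intended dose, replace the line with 50-300 micrograms IV. Write the unit in full so that it does not depend on a symbol. If the PDF already prints micrograms, nothing in the dose needs correcting.

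The cost is one check and, if confirmed, a one-line protocol correction with IRB notification. Design, sample size, schedule and analysis stay as they are.
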